### 2.1 Introduction

Case management with highly effective antimalarial drugs has contributed to a decrease in malaria morbidity and mortality. However, preventive administration of antimalarial drugs is also recommended for use in selected high-risk populations, irrespective of malaria infection status, both to treat any unrecognized Plasmodium infections and to prevent new ones. These preventive treatments prevent

or cure undetected malarial illness with the goal to achieve therapeutic drug levels in the blood throughout the period of greatest risk (9). WHO strongly recommends with high-certainty evidence the following malaria chemo preventive therapies: SMC, intermittent preventive treatment in infants (IPTi), and intermittent preventive treatment in pregnancy (IPTp)(1).

Since malaria chemoprevention is administered to otherwise healthy infants, children, and pregnant women (who are either parasite-free or have circulating parasites but are asymptomatic), treatments must be highly safe and well tolerated. PQP has not shown any teratogenic liabilities and is therefore expected to be a potential safe option for malaria prevention in pregnant women and women of child-bearing potential (WOCBP) which is a key asset towards malaria eradication.

Sulfadoxine-pyrimethamine (SP) is recommended for IPTp along with the antenatal care visits starting from the second trimester of pregnancy and IPTi along with infant vaccination taking place usually at 10 weeks, 14 weeks and 9 months of age. Sulfadoxine-pyrimethamine plus amodiaquine (SPAQ) is recommended for SMC as a monthly administration during the malaria season for three to four consecutive months to children between three months and five years of age in areas of highly seasonal malaria transmission (1). In this context, SPAQ demonstrated a protective efficacy of >80 % in Burkina Faso (4).

### **2.1.1 General treatment / Administration**

PQP exposure from the currently approved hard tablet in healthy adult participants, increased approximately 3-fold with high fat/high calorie meals (European Medicine Agency). However, no significant impact on PQP exposure was observed with local low-fat meals in South-East Asia (6, 7, 8). The present new child-friendly, taste-masked dispersible granule formulation of PQP is being developed to increase bioavailability and minimize the food effect. For SMC (and other use cases), no food restrictions are ideal, as food intake of young children before and after drug administration varies and cannot be controlled. In the present study, the PK profile of a PQP oral dispersible granules (the paediatric formulation prototype) will be evaluated relative to the PQP hard tablet formulation in fasting conditions (Part 1), and when administered with different food restrictions (Part 2) to assess BA/FE, in healthy adults.

### **2.1.2 Efficacy**

Not applicable for the present BA/FE trial.

### **2.1.3 Mechanism of action, clearance and pharmacokinetics**

PQP's mechanism of action is unknown, but it likely mirrors that of chloroquine, a close structural analogue. Chloroquine binds to toxic haem (derived from the patient's haemoglobin) within the malaria parasite, preventing its detoxification via a polymerisation step (10) PQP is a highly lipophilic compound, is highly bound to proteins (>99%) and tends to accumulate in red blood cells. In humans, PQP has a Tmax of approximately five hours after hard tablet administration. PQP is mainly metabolized by CYP3A4 and to a lesser extent by CYP2C9 and CYP2C19. PQP is also a CYP3A4 inhibitor, and a clinical study of Eurartesim® with midazolam showed a modest increase in the exposure of midazolam (<two-fold)(10). The terminal elimination half-life of PQP is around 22 days for adult patients.

### **2.1.4 Safety and tolerability**

Through their extensive use in many African and South-East Asian countries, the safety and tolerability of PQP for the treatment of uncomplicated malaria when combined to DHA, is well established. Safety data from a European registry have also been recently published for DHA-PQP (5).

PQP as a combination antimalarial with DHA is well tolerated in both adults and children, with the main AEs reported being gastrointestinal disturbances such as nausea/vomiting, abdominal pain and diarrhoea (9, 10).

### 2.1.5 Safety profile and potential risks

Although transient asymptomatic alanine aminotransferase/aspartate aminotransferase (ALT/AST) elevations have been described, including in Phase 1 participants, these are generally mild in severity and considered as uncommon. PQP is known to induce QTc prolongation in human participants (11, 12). The following aspects of the PK and adverse event (AE) profiles of PQP, were considered in determining the Inclusion and Exclusion criteria and in designing the tolerability and safety monitoring of this study:

- PQP is known to cause a QTc interval prolongation, and this effect is concentration-related,
- PQP has a terminal elimination half-life of approximately 22 days, however, approximately 1% of the plasmatic Cmax is predicted at 672 hours (i.e. 28 days) after the administration of 1280 mg in healthy adults (13). Therefore, a follow-up of 30 days is considered acceptable to ensure that possible delayed effects on safety laboratory tests are appropriately documented.

As precautionary measures pertaining to QTc effects of PQP, the European Medicines Agency (EMA) has advised that:

- DHA-PQP (Eurartesim®), not be administered with a meal to avoid food-induced increase in PQP Cmax and consequently possible clinically relevant QTc prolongation,
- Baseline and post-dose electrocardiograms (ECGs) be obtained,
- Recent exposure to concomitant drugs known to induce QTc prolongation be avoided (10,14).

Therefore, during this study, healthy participants with risk factors for QTc prolongation will be excluded and enrolled participants will be monitored for QTc effects through ECG recording.

Clinical monitoring will include periodic biochemistry and haematology measurements as well as regular physical examination and AE recording.

Participants will remain in the Unit under medical supervision until 48 hours following the investigational medicinal product (IMP) administration and will be followed up to Day 30 (+/-1 day).

Despite significant human Ether-a-go-go Related Gene (hERG) blockade with PQP and a mean prolongation of 15-20 msec (fasting state) demonstrated in multiple Phase 1 studies, a meta-analysis has recently concluded that patients treated with the registered three-day regimen of DHA-PQP are not at higher risk of torsades de pointes (TdP), ventricular tachycardia or other arrhythmias when compared with the normal population (14). Based on these observations, although inducing a QTc prolongation that exceeds the ICH/FDA regulatory threshold of 10 msec, PQP is currently not considered as a torsadogenic drug provided it is taken in a fasted state and other clinical risk factors for QTc prolongation (including electrolyte imbalance and/or concomitant medications) are appropriately controlled (15). Healthy volunteers with long QTc are also excluded from clinical trials.

### 2.2 Justification for the dosage and dosage plan

This is a single-dose study and is considered sufficient to provide early assessment of the bioavailability of the PQP dispersible granules formulation (fasted) relative to the PQP hard tablet formulation (fasted) and understand the impact of food intake on the dispersible granules formulation. The rationale for the selected dose includes:

- As the new formulation is intended to have an increased bioavailability, a lower dose of 320 mg for the PQP dispersible granules formulation (test) has been selected. For comparison purpose, the

same dose level of 320 mg PQP has been selected for the hard tablet (reference); both administered in fasting conditions (Part 1). This compares to the approved daily dose of 960 mg PQP in tablet of Eurartesim® administered over 3 days in adult subjects dosed in fasting conditions.

- In the second study part, and based on the PK results of Part 1, it is intended to administer the same dose level of 320 mg PQP dispersible granules concomitant with different fed conditions. However, if from Part 1 of the study it is shown that PQP dispersible granules formulation provides a significant improvement in  $C_{max}$  values in the fasted state, this dose level may be adjusted for Part 2, in order to take into account a potential 3-fold increase in exposure which is the observed food effect when film-coated tablets (Eurartesim®) are administered with a high fat/high calorie meal. Such dose adjustment will be based on the safety and preliminary PK interim results of the granule formulation in the fasted state. The PQP dose selected in Part 2 (as dispersible granules formulation) will take into account a 3-fold factor increase in exposure when administered with food (see above) with such predicted exposure in the presence of food being not higher than after the administration of 960 mg PQP in tablet of Eurartesim® in adult subjects dosed in fasting conditions. Furthermore, sufficient data will be available to address key questions on both, safety and PK parameters to enable the review and recommendation by the SRC for the optimal dose of the granule formulation to be administered in Part 2.

### 3 OBJECTIVES AND PURPOSE

The present pilot BA/FE study aims to assess the relative bioavailability and food effect on the systemic exposure of a new child-friendly, taste-masked dispersible granule formulation of PQP among healthy adults. In addition, PK and safety profiles will be further evaluated and documented.

#### 3.1 Study rationale and objectives

##### 3.1.1 Study rationale

The present new child-friendly, taste-masked dispersible granule formulation of PQP is being developed to increase bioavailability and minimize the impact of food on PK exposure and consequently QTc effects. In healthy adult participants, the currently approved hard tablet had an approximately 3-fold increase in PQP exposure when administered with a high fat/high calorie meal (10). However, a local low-fat meal in South-East Asia had no significant impact on PQP exposure (6, 7, 8).

In the present study performed in healthy subjects, the PK profile of a PQP oral dispersible granules formulation (the paediatric formulation prototype) will be compared to the PQP hard tablet formulation in fasting conditions (Part 1), and when administered in different fed states (Part 2) to assess the BA/FE. This assessment is important since for SMC (and other use cases), food restrictions for treatment with oral PQP are not ideal, as food intake of young children before and after drug administration varies and cannot be controlled.

This study will establish whether the BA of the child-friendly dispersible granules formulation of PQP is improved in comparison to PQP hard tablet in fasting conditions and will inform dose selection of the granule formulation.

The study will also determine whether there is an effect of food on the exposure of PQP from the child-friendly dispersible granule formulation, and whether the magnitude of the food effect is similar, or decreased compared to the PQP hard tablet:

- Studies with a high fat meal are required by Regulators to determine the “worst case food effect”. In addition, as recognized by regulators (FDA): when drug administration with a high-fat meal causes unacceptable toxicity or a loss of drug efficacy, a low-fat meal can have less or no impact on systemic exposures, improve patient compliance, and alleviate localized gastric irritation. In these circumstances, and assuming that no clinically relevant safety impact is expected, administration of the drug with a low-fat meal may be more advantageous to patients.
- Given the low-fat content of standard meals within endemic regions, the food effect in African and Asian patients and in particular children in areas of SMC will likely be decreased.

##### 3.1.2 Primary objective

- To determine the relative bioavailability of a single oral dose of PQP dispersible granule formulation (Test) as compared to PQP hard tablet formulation (Reference) in the fasted state.

##### 3.1.3 Secondary objectives

- To assess the effect of different types of meal composition on the PK of single doses of PQP dispersible granule formulation in healthy adult participants.
- To further evaluate the PK of a single oral dose of PQP granule formulation in the fasted state and different fed states in healthy adult participants.

- To further document safety/tolerability of PQP in healthy adult participants.

### **3.1.4 Exploratory objectives**

- To further document PQP metabolite profiling and PK depending on results of former study (optional objective) as well as the results of genetic testing of CYP450s polymorphism (optional).
- To evaluate the palatability of the new PQP granule formulation in healthy adult participants.

### **3.2 Scientific justification and rationale of study population**

This study includes male and female participants aged 18 to 55 years at the date of signing informed consent who are residing within and surrounding areas of Bagamoyo town. Both genders will be enrolled to generate data on both sexes. Data from this trial will support development of a new piperaquine formulation with a reduced impact of food which will be more practical for paediatric population.

## 4 STUDY DESIGN

This is a randomized, open label, parallel-design study to evaluate the PK profile and relative bioavailability of single dose of a PQP oral granule formulation dispersed in water (test) as compared to the PQP hard tablet formulation (reference) in fasting conditions (Part 1) and to assess the BA/FE of the PQP dispersible granules formulation when administered with different food restrictions (Part 2) among African participants residing in Tanzania, in Bagamoyo Town and surrounding areas. A total of sixty (60) healthy adult participants (male and female) will be enrolled in Part 1 and Part 2.

- **Part 1:** PQP tablet / dispersible granule administered in **fasting condition** of at least 10 hours
  - Group 1: PQP hard tablet, 320 mg (N=12)
  - Group 2: PQP dispersible granule, 320 mg (N=12)
- **Transition to Part 2:**
  - To minimize the risk to healthy participants, a decision on transitioning from Part 1 to Part 2, will be taken by the Safety Review Committee (SRC) see Section 13.7, based on the safety and preliminary PK interim report of the granule formulation, compared to the PQP hard tablet, with safety data obtained up to Day 15 and PK data obtained up to Day 8. If necessary, doses may be readjusted for the Part 2 in order to assess the food effect. Description for the rationale and oversight related to the potential for dose adjustment is provided in Section 2.2.
- **Part 2:** PQP dispersible granule administered in **fed conditions (planned as 320 mg)**
  - Group 3: High-fat meal (N=12)
  - Group 4: Low-fat meal representative of African diet (N=12)
  - Group 5: Whole milk 250 ml (N=12)

In summary: Participants will be screened within a window of  $\leq$  45 days prior to in-house admission on Day -1. Each participant will be admitted to the trial unit on Day -1, and after a new eligibility check, will receive a single dose of PQP on Day 1 and will be discharged on Day 3 (a total 4 in-house days). Participants will attend the trial unit clinic for outpatient visits on Days 8, 15, 22 and 30. Details of procedures and parameters to be assessed at each study time points are outlined in Section 7 (Study Assessments and Visits) and summarized in Section 4.4 (Schedule of events).

### 4.1 Primary and secondary endpoint

#### 4.1.1 Primary endpoint

- Relative bioavailability (Frel) using the ratio of the geometric means for the dispersible granule (test) over the hard tablet (reference) in fasted state for area under the plasma concentration-time curve from time zero to 72 hours (AUC0-72h), area under the plasma concentration-time curve from time zero to last detectable plasma concentration (AUC0-t), area under the plasma concentration-time curve from time zero to 168 hours (AUC0-168h), area under the plasma concentration-time curve from time zero extrapolated to infinity (AUC0-∞), and Maximum plasma concentration (Cmax)(see Section 10 for further details).

#### 4.1.2 Secondary endpoints

- PK parameters for the hard tablet (fasted) and the dispersible granule formulations (fasted and fed); Cmax, AUC0-24h, AUC0-72h, AUC0-t, AUC0-168h, AUC0-∞, time to maximum plasma concentration (Tmax), terminal elimination rate constant (λz), terminal elimination half-life (t1/2), apparent volume of distribution during the terminal phase (Vz/F), apparent total plasma clearance

(Cl/F), and percentage of AUC that is due to extrapolation from tlast to infinity (%AUCExtrap) (see Section 10 for further details).

- Occurrence of AEs including serious adverse events (SAEs) from the IMP administration throughout the entire study period (up to Day 30).
- Findings at different time points from:
  - Physical examination, vital signs, clinical laboratory safety parameters, 12-lead ECG parameters. See Section 8 for specific parameters and time points.

## 4.2 Measures to minimize bias

### 4.2.1 Randomization

Healthy adult participants (male and female) will be randomly allocated to one of the 5 following treatment groups, dosing will be carried out in the fasted or fed state:

- During the study part 1, participants for fasted conditions will be randomly allocated to either group 1 (n=12) or group 2 (n=12), in order to assess the relative bioavailability of the dispersible granules formulation as compared to hard table formulation.
  - Randomization will occur in blocks of 2 (each block contains 1 assignment from each of the groups 1 and 2). Dosing under fasting conditions is detailed in Section 6.2.1.
- During the study part 2, participants for fed conditions will be randomly allocated to either group 3 (n=12), 4 (n=12) or 5 (n=12), in order to assess the food effect after dosing of PQP dispersible granules formulation.
  - Randomization will occur in blocks of 3 (each block contains 1 assignment from each of the groups 3, 4 and 5). Dosing under fed conditions is detailed in Section 6.2.2.

A computer-generated randomization schedule (produced by IQVIA) will be used and will be accessible only to the site delegated study staff who will prepare the treatment for each participant according to the randomization allocation. Specific instructions will be detailed in the relevant site manual.

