Objective(s)	
Primary objective: To determine the relative bioavailability of a single oral dose of PQP dispersible granule formulation (Test) as compared to PQP hard tablet formulation (Reference) in the fasted state.
 
Secondary objectives:
 

• To assess the effect of different types of meal composition on the PK of single doses of PQP dispersible granule formulation in healthy adult participants.

• To further evaluate the PK of a single oral dose of PQP granule formulation in the fasted state and different fed states in healthy adult participants.

• To further document safety/tolerability of PQP in healthy adult participants.

 
Exploratory objectives:
 

• To further document PQP metabolite profiling and PK depending on results of former study (optional objective) as well as the results of genetic testing of CYP450s polymorphism (optional).

• To evaluate the palatability of the new PQP granule formulation in healthy adult participants.

Outcome (s)	
Relative bioavailability:
 
Using the ratio of the geometric means for the dispersible granules [test] over the hard tablet [reference] in fasted state for <math>AUC_{0-72h}</math>, <math>AUC_{0-t}</math>, <math>AUC_{0-168h}</math>, <math>AUC_{0-\infty}</math>, and <math>C_{max}</math>.

	
Using the ratio of the geometric means for the dispersible granules between fed [high-fat meal, low-fat African meal, and milk] and fasted for <math>AUC_{0-72h}</math>, <math>AUC_{0-t}</math>, <math>AUC_{0-168h}</math>, <math>AUC_{0-\infty}</math>, and <math>C_{max}</math>.
 
Safety:
 
Occurrence of adverse events (AE) including serious adverse events (SAE) from the investigational medicinal product (IMP) administration throughout the entire study period (up to Day 30 after IMP administration).

Study Design	
Single centre, randomized, open label, single dose, parallel-group design performed in two sequential parts.
 
A total of sixty (60) healthy adult participants (male and female) will be enrolled in this study (24 subjects in Part 1 and 36 subjects in Part 2). Efforts will be made to ensure a reasonable gender balance.

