### 4.2.2 Blinding

The trial will be open-label i.e., participant, investigator and sponsor will be unblinded to treatment and meal conditions assignation. Therefore, after treatment allocation by the site pharmacist according to the randomisation schedule, the study investigators will be provided with the explicit details related to the treatment (Part 1) or feeding conditions (Part 2).

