### **7.3.2 In-house visit procedures**

Overall, in-house visits will cover the following main procedures / activities:

- Admission of eligible participants to the trial facility one day prior to study treatment (Day-1)
  - Number and schedule of participants to be dosed in a single day will depend on a combination of factors targeted to optimize implementation of study assessments without risking the safety of participants or losing quality. The overall tentative study schedule will be used as a reference for future scheduling.
  - Replacement of participants during the in-house visits is described in Section 5.4.
- Random treatment allocation and administration of study IMP on the following day (Day1)
- Post IMP continuous assessments and safety monitoring (Day1, Day2)
- Completion of in-house assessments and discharge from the trial facility (Day3).

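### Fixed, printed blocks of 2 and 3 in an open-label single-site trial let up to half of Part 1 and up to a third of Part 2 allocations be deduced, which weakens allocation concealment

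*Protocol*

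**What the plan says.** Protocol 4.2.1 fixes the block structure. For Part 1: "Randomization will occur in blocks of 2 (each block contains 1 assignment from each of the groups 1 and 2". For Part 2: "Randomization will occur in blocks of 3 (each block contains 1 assignment from each of the groups 3, 4 and 5". SAP 4.2 says the same. The numbers per part are "24 subjects in Part 1 and 36 subjects in Part 2" (Protocol 1.6).

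The synopsis describes the design as "Single centre, randomized, open label, single dose, parallel-group design performed in two sequential parts". Protocol 4.2.2 adds that "participant, investigator and sponsor will be unblinded to treatment and meal conditions assignation", and that once the site pharmacist has allocated, "the study investigators will be provided with the explicit details related to the treatment (Part 1) or feeding conditions (Part 2".

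Some protection is stated. The schedule "will be accessible only to the site delegated study staff who will prepare the treatment for each participant" (Protocol 4.2.1). Eligibility is reviewed at admission on Day -1 (7.3.2.1). The step that follows admission is "Random treatment allocation and administration of study IMP on the following day (Day1" (7.3.2), and 7.3.2.2 lists randomisation last among the pre-dose procedures.

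Three things are not stated: how many participants are dosed per day (7.3.2 leaves this open), the order in which a day's participants are randomised, and any variation or withholding of block size. Protocol 4.2.1 refers further instructions to a site manual that is not among the documents.

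**The concern.** A block of 2 is the smallest possible for two arms. Once the first member's formulation is known, the second is certain. In a block of 3, the third is certain once two are known, and the second is a 1-in-2 guess. Because the sizes are printed and past allocations are disclosed at one site, the people who decide on enrolment and scheduling can make this deduction without seeing the list.

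What is at stake is the composition of the arms, not the assay. If the next assignment is known, the choice of who takes it can be influenced, even with good intentions. The synopsis asks for a reasonable gender balance, yet randomisation is not stratified by sex. Weight can range widely (at least 50 kg, BMI 18 to 30). The primary model in SAP 18.1.2 has treatment as its only fixed effect, so an imbalance in weight or sex would pass unadjusted into the geometric mean ratio. Part 1 PK also feeds the decision on moving to Part 2 (Protocol 2.2 and 4).

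**Working it through.** **Inputs.** Block sizes 2 and 3, one assignment per group (Protocol 4.2.1, SAP 4.2). Participants: 24 in Part 1 and 36 in Part 2 (Protocol 1.6). Investigators are told each allocation (Protocol 4.2.2). The number dosed per day is not given, so 1 to 8 is assumed below to show the range.

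**1. The plan's own totals.** 12 blocks × 2 = 24; 12 blocks × 3 = 36; 24 + 36 = 60. This matches the stated enrolment.

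**2. Maximum deducible share.** An allocation is forced when only one group remains in the open block. With k groups and m assignments per group in a block, the expected forced share is 1/(km − m + 1).
- Part 1 (k = 2, m = 1): 1/2, i.e. 12 of 24 = 50%.
- Part 2 (k = 3, m = 1): 1/3, i.e. 12 of 36 = 33.3%.
- Both parts: 24 of 60 = 40%.

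These are maxima. They require one-at-a-time allocation, with every earlier result seen before the next person is committed.

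**3. Best-guess rate under the same condition.** Part 1: (1/2 + 1)/2 = 75%. Part 2: (1/3 + 1/2 + 1)/3 = 61.1%.

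**4. Share already forced at the Day -1 decision.** Suppose all earlier cohorts have been revealed. One allocation is then forced at admission whenever a cohort starts with exactly one slot left in the open block. For example, Part 1 cohorts of 3 start after 0, 3, 6, 9, 12, 15, 18 and 21 participants. The four odd starts each leave one slot, giving 4/24.

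| Assumed cohort size | Part 1 | Part 2 |
|---|---|---|
| 1 | 12/24 = 50% | 12/36 = 33.3% |
| 2 | 0% | 6/36 = 16.7% |
| 3 | 4/24 = 16.7% | 0% |
| 4 | 0% | 3/36 = 8.3% |
| 5 | 2/24 = 8.3% | 3/36 = 8.3% |
| 6 | 0% | 0% |
| 7 | 2/24 = 8.3% | 2/36 = 5.6% |
| 8 | 0% | 2/36 = 5.6% |

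Within a cohort, the last slot of each block can still be deduced on Day 1 if allocations are made and seen in sequence.

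**5. Larger blocks, even if their sizes became known.**
- Part 1: size 4 (m = 2) gives 1/3 = 33.3%; size 6 (m = 3) gives 1/4 = 25%.
- Part 2: size 6 (m = 2) gives 1/5 = 20%; size 9 (m = 3) gives 1/7 = 14.3%.
- The sizes fit the totals: 4 + 4 + 4 + 6 + 6 = 24 and 6 + 6 + 6 + 9 + 9 = 36.

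**6. Illustration of the stakes (assumed values).** Exchanging one pair between two arms of 12 shifts the log ratio by 2d/12, where d is the pair's log difference in exposure. If the two exposures differ 1.25- to 1.5-fold, one exchange moves the ratio by 1.25^(1/6) to 1.5^(1/6), about 4% to 7%. Three exchanges in the same direction move it by 1.25^(1/2) to 1.5^(1/2), about 12% to 22%. The documents give no variability figure, so this shows scale only.

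**The case against.** A reader might infer that half of Part 1 and a third of Part 2 are known in advance and that concealment is defeated. The documents do not support that. The list is restricted to the staff who prepare treatment, the pharmacist allocates, and investigators are told afterwards. Eligibility is reviewed on Day -1, before Day 1 allocation, and this does help: with suitable cohort sizes nothing is forced when the eligibility decision is taken. The opening slot of every block stays unpredictable.

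Nor are the obvious routes for steering as open as they look. Backups stand in for participants withdrawn before fasting starts (Protocol 5.4), so before Day 1 allocation; matching one to a known arm would need a block left open from an earlier dosing day. Replacements need agreement between investigator and sponsor (5.4, 6.6). If a replacement takes the same arm, that arm is known whatever the block size, so larger blocks would not help. No passage says who sets the order of randomisation.

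It can also be said that the endpoint is laboratory-measured, that staff would have to foresee an individual's exposure and have a reason to act on it, that Protocol 10.1 tests no hypothesis, and that SAP 11 tabulates weight and sex by group, so gross imbalance would show.

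Most of this stands, and it limits the claim. Two things do not answer it. An objective assay protects measurement, not who enters each arm. And the protection from cohort size is accidental, because neither cohort size nor allocation order is fixed in the documents.

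**Conclusion.** The point holds as a weakness, not a failure, of concealment. Concealment is lost for the last slot of a block when earlier allocations in that block have been seen, and it is partly eroded for the second slot in Part 2. The ceiling is 50% of Part 1 and 33% of Part 2. The share known at the Day -1 decision lies between 0% and those ceilings, depending on a cohort size that the plan does not state. Nothing in the documents shows that steering would occur.

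Part 1 matters most, because it is the primary randomised comparison. In Part 2 each fed group is compared with Group 2 from Part 1 (Protocol 10.9, SAP 19.1.2). Those contrasts cross parts and are not protected by Part 2 randomisation, which secures only comparability between the meal groups.

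The conclusion assumes that the unseen site manual adds no safeguard. The change is worth making because it is cheap.

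**What to change.** For any part not yet randomised:

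- In Protocol 4.2.1 and SAP 4.2, replace the fixed blocks with randomly varying block sizes. Keep the sizes out of both documents and withhold them from site investigators. For example, use sizes 4 and 6 summing to 24 in Part 1, and 6 and 9 summing to 36 in Part 2. Even if the sizes became known, the deducible share would fall to 25–33% in Part 1 and to 20% or less in Part 2.
- Fix the allocation order of each dosing-day cohort by screening number, once the Day -1 eligibility review is complete and before any of that cohort's allocations is revealed.

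The cost is a new computer-generated list and a few sentences of protocol and SAP text. The downside is slightly looser balance within a dosing day.

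For any part already randomised, report baseline weight and sex by arm beside the PK comparison (SAP 11 already plans the tables) and state the predictability of the blocks as a limitation. This may be the case that applies: the synopsis planned last participant out for December 2023 and the SAP is dated 19 December 2023, but the documents do not give the actual status.
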